10 ADMINISTRATIVE CONSIDERATIONS

10.1 Study Administrative Structure

Details of contract research organizations, central laboratories and other participating organizations will be provided in the laboratory manual supplied to each site.

10.2 Institutional Review Board/Ethics Committee Approval

Good Clinical Practice requires that the clinical protocol, any protocol amendments, the IB, the ICF, and all other forms of subject information related to the study and any other necessary documents be reviewed by an Independent Review Committee (e.g., an IRB).

10.3 Ethical Conduct of the Study

In accordance with applicable country-specific regulations, the sponsor will obtain approval from the appropriate regulatory authority(ies) prior to initiating the study in that country. This study will be conducted in accordance with the protocol, all ICH and GCP regulations governing clinical study conduct, ethical principles that have their origin in the Declaration of Helsinki, and all applicable local laws and regulations. The Investigator must assure that the study is conducted in accordance with prevailing local laws and customs.

It is the Investigator's responsibility to ensure that this protocol is reviewed and approved by the appropriate IRB/EC. The IB must be provided to the IRB/EC.

The IRB/EC must also review and approve the site's ICF and any other written information provided to the subject and any advertisement that will be used for subject recruitment prior to its use.

10.4 Subject Information and Consent

The Investigator or his/her qualified designee will explain the nature of the study to the subject, and answer all questions regarding this study, prior to obtaining informed consent.

The Investigator or his/her qualified designee will obtain informed consent from each subject enrolled in the study, in accordance with the Declaration of Helsinki, the current version of the ICH guidelines and the local laws and applicable regulatory requirements.

It is the responsibility of the Investigator to assure that the subject or LAR has consented and has signed the ICF before any activity or treatment is undertaken which is not part of routine care. The subject and/or LAR will receive a signed copy of the ICF and the original will be retained in the site study records. The Investigator or his/her designee will ensure documentation of the consent discussion in the subject's medical record/source documents. The decision by the subject and/or LAR to participate in the study is entirely voluntary. The Investigator or designate must emphasize to the subject and/or LAR that consent regarding study participation may be withdrawn at any time without penalty or loss of benefits to which the subject is otherwise entitled.

If the ICF is amended during the study, the Investigator must follow all applicable regulatory requirements pertaining to approval of the amended ICF by the IRB and use of the amended form (including for ongoing subjects).

10.5 Subject Confidentiality

Subject confidentiality will be strictly held in trust by the participating Investigators, their staff, the sponsor and their authorized representatives. This confidentiality is extended to cover testing of biological samples in addition to the clinical information relating to participating subjects.

The study protocol, documentation, data, and all other information generated will be held in strict confidence. No information concerning the study or the data will be released to any unauthorized third party, without prior written approval of the sponsor.

Authorized representatives of the sponsor, the designated contract research organization (if applicable), the study monitor, employees of government authorities such as the US FDA or other government authorities, and members of the IRB may inspect all documents and records required to be maintained by the Investigator, including but not limited to, medical records (office, clinic, or hospital) and pharmacy records for the subjects in this study. The clinical study site will permit access to such records.

No information that would permit the identification of a specific individual will be provided for entry into the study database or study report. Study documentation submitted to the sponsor will identify study participants by study code and initials. The Investigator will keep a separate confidential enrollment log that matches identifying study codes with the subjects' names and residencies.

10.6 Study Monitoring

The sponsor and/or its designee are responsible for monitoring the study in accordance with the requirements of the ICH/GCP, and in accordance with written SOPs and the Clinical Monitoring Plan.

The study will be monitored by the sponsor or designee at all stages of study conduct from inception to completion in accordance with current ICH/GCP. The Investigator will allocate adequate time for such monitoring activities. This monitoring will be in the form of site visits and other communication and will include review of original source documents, eCRFs, facilities and equipment, recruiting, record-keeping, protocol adherence, data collection, AE reporting, and other factors. The frequency of these visits will depend upon the progress of the study.

The Investigator will ensure that the monitor or other compliance or quality assurance reviewers are given access to all the above noted study-related documents and study related facilities (e.g., pharmacy, diagnostic laboratory), and has adequate space to conduct the monitoring visit.

10.7 Case Report Forms and Study Records

Source documents are defined as original documents, data and records. This may include hospital records, clinical and office charts, laboratory data/information, subjects' diaries or evaluation checklists, pharmacy dispensing and other records, recorded data from automated instruments, microfiches, photographic negatives, microfilm or magnetic media, and/or x-rays.

Data collected during this study must be recorded on the appropriate source documents. All source documents should be completed in a neat, legible manner to ensure accurate interpretation of data.

Data capture and management will be consistent with applicable ICH/GCP guidelines.

All data collected during the study for subjects who are enrolled will be recorded in an individual, subject-specific eCRF as part of an EDC system. The sponsor or designee will provide training to the investigative site on the EDC system and eCRFs. All eCRFs will be completed in a timely manner as data are available in the source for each subject. As EDC will be utilized, instructions, training records, and a log will be maintained to identify the designated site personnel who can enter data and/or sign off on an eCRF.

A subject eCRF must be completed for each subject who signs a consent form and is randomized. All data generated from external sources, (e.g., central laboratory results), will be integrated with the subject eCRF data through programming or other data integration techniques.

All eCRFs should be completed within 5 business days of the visit to enable the study monitor to review the subject's status throughout the course of the study in real time. Queries also should be resolved in a timely manner.

The Investigator will sign and date the indicated places on the eCRF via the EDC system's electronic signature. These signatures will indicate that the Investigator reviewed the data on the eCRF, the data queries, and the data clarifications and agrees with the content.

10.8 Protocol Deviations

Protocol deviations are any intentional or unintentional change from an IRB approved protocol that are not approved by the IRB prior to initiation of the change and are collected in EDC.

Major protocol deviations are deviations that result in increased risk to subjects, affect the rights, safety, or welfare of the subjects or affect the integrity of the study.

Major protocol deviations may include but are not limited to deviations from the inclusion/exclusion criteria, informed consent deviations, concomitant medication restrictions, dosing non-compliance, and any other protocol requirement that results in a significant added risk to the subject or has an impact on the quality of the data collected or the outcome of the study.

The sponsor requires that all major protocol deviations be reported to the IRB. In addition, the Investigator is responsible for adhering to his/her IRB's protocol deviation reporting requirements.

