### 5.4 Pharmacokinetic Population

The PK population will include all subjects who are randomly assigned to treatment, receive at least 1 dose of study drug, have no major protocol deviations, have at least 1 PK data point at BL, and sufficient measureable serum calcifediol or paricalcitol concentrations to facilitate the calculation of at least 1 postdose PK parameter using validated methods. Presentation of data will use the actual treatment. In cases where a subject's dosing compliance is found to be an issue, PK parameters may not be calculated for that subject.

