### **6.2 Protocol Deviations**

Major protocol deviations will be captured as a log by the clinical research coordinator, exported into a clinical dataset, and presented in a data listing.

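### The PK population excludes every subject with a major protocol deviation, whether or not the deviation affects PK, so valid profiles can be lost

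*Protocol*

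**What the plan says.** Protocol 9.4 and SAP 5.4 define the PK population in the same terms. Subjects must be randomised, receive at least one dose, "have no major protocol deviations, have at least 1 PK data point at BL", and have enough measurable calcifediol or paricalcitol concentrations for at least one post-dose parameter. SAP 5.4 adds that parameters may be withheld where dosing compliance is an issue.

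The visible definition of a major deviation is in Protocol 10.8: "deviations that result in increased risk to subjects, affect the rights, safety, or welfare of the subjects" "or affect the integrity of the study". The listed examples include eligibility deviations and "informed consent deviations, concomitant medication restrictions, dosing non-compliance", and end with any other requirement that adds significant risk or "has an impact on the quality of the data collected or the outcome of the study". The same section gives the term a reporting use: "The sponsor requires that all major protocol deviations be reported to the IRB".

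SAP 6.2 describes how the information reaches the analysis: "Major protocol deviations will be captured as a log by the clinical research coordinator". The log is then exported to a dataset and listed.

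The visible calcifediol PK tables (SAP Appendix A, 14.2.1) and the between-arm model (SAP 7.3) use the PK population. The per-protocol definition in SAP 5.2 and part of Protocol 9.4 are redacted, so statements about what is defined apply to the visible text only.

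**The concern.** One term does two jobs. For reporting to the IRB, a broad definition is sensible. As a bar to a PK analysis set it is not, because several of its limbs say nothing about whether a concentration was validly obtained after a known dose. A subject dosed in the phase 1 unit on Days 1 and 29, with complete samples, can be excluded for a consent or safety-procedure deviation.

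PK is a named objective, and the arms have about 20 subjects each. Discarding valid profiles costs precision. It also removes subjects after randomisation for reasons that are not PK reasons.

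**Working it through.** **1. The rule and the definition, side by side.** The population rule turns on one condition, no major deviation. The definition in Protocol 10.8 joins its limbs as alternatives, so any one is enough:

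- Limbs and examples that can bear on PK: study integrity, dosing non-compliance, restricted medication, data quality, and some eligibility failures.
- Limbs and examples that need not bear on PK: increased risk, rights, welfare, consent.

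Nothing in the visible text limits the PK exclusion to the first group.

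**2. Subject against profile.** SAP 7.2 fixes the data window for each set of parameters.

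| Regimen | Day 1 parameters use | Day 29 parameters use |
|---|---|---|
| Daily arms | 24 h after the Day 1 dose | 24 h after the Day 29 dose (to Day 30) |
| Monthly arms | 28 days after the Day 1 dose | to Day 57 |

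In a daily arm, a deviation first occurring between Day 31 and Day 57 lies outside both windows, yet the subject loses both profiles. In a monthly arm, a deviation after Day 29 lies outside the Day 1 window, yet it removes that profile too. This needs no assumed rate.

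**3. Precision.** The plan gives no figure to reproduce: there is no formal sample size (Protocol 9.2, SAP 3.2) and no deviation rate. The only input from the documents is about 20 subjects per arm. The losses below are assumptions.

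If k of 20 are lost in every arm, the standard error of a two-arm contrast rises by √(20/(20−k)) − 1:

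- k = 1: √(20/19) − 1 = 2.6%
- k = 2: √(20/18) − 1 = 5.4%
- k = 3: √(20/17) − 1 = 8.5%

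The 95% confidence interval half-width in SD units, t(0.975, 4n−5) × √(2/n), allows for treatment and the baseline covariate. It goes from 0.630 at n = 20 to 0.647, 0.665 and 0.685 at n = 19, 18 and 17, which is +2.7%, +5.6% and +8.8%.

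For scale, if 5% to 10% of subjects had a major deviation that left PK valid (assumed), 80 × 0.05 = 4 to 80 × 0.10 = 8 profiles would go. The chance that an arm of 20 loses at least one is 1 − 0.95^20 = 64% to 1 − 0.90^20 = 88%.

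**4. Bias, as illustration only.** With simulated lognormal exposures, 20 per arm and 2 lost, the change in the arm mean is:

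| How the 2 are lost | CV 30% | CV 50% |
|---|---|---|
| At random | none | none |
| Chance of loss rising with exposure squared | −1.8% | −5.0% |
| The 2 highest exposures | −6.3% | −11.1% |

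The CVs and loss mechanisms are assumptions. The documents do not say which row applies.

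**The case against.** The other side has real points.

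- A reader might infer that the definition of major is purely about risk, rights and consent. It is not. The defining sentence goes on to study integrity, and the examples name dosing and data quality. The fair criticism is that the definition is too broad for this use.
- Protocol 10.8 says major deviations may include consent deviations. A trivial form error would still have to meet the definition.
- A reader might infer that nobody reviews the coordinator's log. Protocol 8 and 10.6 describe sponsor data review and monitoring for protocol adherence. What the visible text lacks is narrower: a pre-lock assessment of PK relevance made without sight of the concentrations.
- A reader might infer that exclusions will track toxicity, for example through a required dose change that was not made. Protocol-directed reductions, holds and suspensions (Protocol 5.3) are not deviations when followed. The route needs a confirmed abnormal value, a failure to act, classification as major, and a link between toxicity and calcifediol exposure. No frequency is given for any of these steps.
- The PK comparison is exploratory. Protocol 9.11.1 also plans descriptive calcifediol summaries in the ITT population, safety analyses use all dosed subjects, and excluded data and reasons for exclusion are listed.

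All of this limits the size of the point. None of it supplies a PK-relevance criterion. The ITT summaries as visible describe serum calcifediol, and no visible table gives the PK parameters or the SAP 7.3 model outside the PK population.

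**Conclusion.** The point holds in a limited form. As written, the PK population excludes whole subjects for deviations that need not affect PK, and it removes profiles completed before the deviation occurred. Valid profiles can be lost; whether and how many will be lost cannot be told from the documents.

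On an assumed loss of 1 to 3 of 20 per arm, the cost is about 3% to 8% in the standard error. Bias arises only if loss is related to exposure, which is possible but not shown. The visible text does not support a claim that loss will depend on toxicity or differ between arms. Because the fix is cheap and the PK results are a stated objective, the wording should be changed, but the point does not threaten the study's conclusions.

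**What to change.** In Protocol 9.4 and SAP 5.4, replace the condition on major deviations with this one: the subject has no protocol deviation that the sponsor judges, before database lock and without sight of concentration results, to affect the PK evaluation. In addition:

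- Apply it per profile (Day 1, Day 29). Parameters that use both profiles, such as the accumulation ratios and the 56-day exposure, then need both to qualify.
- List the qualifying types: dosing, prohibited medication, sampling, and eligibility failures relevant to PK.
- Handle subjects without valid consent separately. The new wording must not keep their data by default.
- Leave the Protocol 10.8 definition in place for IRB reporting.
- Add a sensitivity summary of the PK parameters and the SAP 7.3 model in all dosed subjects with evaluable concentrations.

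The cost is a short text change in both documents, one review step before lock and a few extra tables. No new data are needed.

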10.9 Data Generation and Analysis

The Investigators are responsible for the accuracy, completeness, and timeliness of the data reported on the eCRF. Study data management, monitoring, statistical analysis, and reporting will be performed by the sponsor using the sponsor's SOPs.

Completed eCRFs are required for each subject enrolled and signed an ICF. Electronic data entry is accomplished through the 21CFR Part 11 compliant remote data capture application,

which allows for on-site data entry and data management. Furthermore, the Investigators retain full responsibility for the accuracy and authenticity of all data entered into the EDC system. The completed dataset and their associated files are the sole property of the sponsor and should not be made available in any form to third parties, except for authorized business representatives or appropriate governmental health or regulatory authorities, without written permission of the sponsor.

Data management, data analysis and programming the submission-ready tables, listings and figures will be responsibility of the sponsor and will be performed and managed per the sponsor's SOPs.

10.10 Retention of Data

In compliance with the ICH/GCP guidelines, the Investigator/institution will maintain all eCRFs and all source documents that support the data collected from each subject, and all study documents as specified in ICH/GCP Section 8, Essential Documents for the Conduct of a Clinical Trial and as specified by the applicable regulatory requirement. The Investigator/institution will take measures to prevent accidental or premature destruction of these documents.

Essential documents must be retained until at least two years after the last approval of a marketing application in an ICH region or at least two years have elapsed since the formal discontinuation of clinical development of the investigational product. These documents will be retained for a longer period if required by the applicable regulatory requirements or by an agreement with the sponsor. It is the responsibility of the sponsor to inform the Investigator/institution as to when these documents no longer need to be retained.

If the responsible Investigator retires, relocates, or for other reasons withdraws from the study, the responsibility of keeping the study records, custody must be transferred to a person who will accept the responsibility. The sponsor or designee must be notified in writing of the name and address of the new custodian. Under no circumstances shall the Investigator relocate or dispose of any study documents before having obtained written approval from the sponsor.

10.11 Financial Disclosure

The principal Investigator and all sub-Investigators are required to provide certification (Financial Disclosure Form) that no financial arrangements with the sponsor have been made where study outcome could affect compensation; that the Investigator has no proprietary interest in the tested product; that the Investigator does not have a significant equity interest in the sponsor; and that the Investigator has not received significant payments of other sorts. The Investigator/sub-Investigator is responsible for informing the sponsor if these circumstances change during the course of the study or within one year of the end of his/her participation in the study.

10.12 Publication and Disclosure Policy

Data derived from the study are the exclusive property of the sponsor. Any publication or presentation related to the study must be approved by the sponsor before submission of the manuscript. After publication of the results of the study, any participating center may publish or

otherwise use its own data provided that any publication of data from the trial gives recognition to the study group. In addition, the sponsor shall be associated with all such publications, it being understood that the sponsor is entitled to refuse the association.

The sponsor must have the opportunity to review all proposed abstracts, manuscripts or presentations regarding this study at least 60 days prior to submission for publication or presentation. Any information identified by the sponsor as confidential must be deleted prior to submission.

APPENDIX 1 SCHEDULE OF EVENTS

	Screen	Wash out	Baseline		Treatment												EOS /ET
Visit	1		2	3	4	5	6	7	8	9	10	11	12	13	14	15	16
Week	-5		-1	-1	1	1	1	2	3	4	5	5	5	6	7	8	9
Day	-70 or -42 to -36	-63 or -35 to -8	-7 to -2	-1	1	2	3	8	15	22	29	30	31	36	43	50	57
					(GCRC)					(GCRC)							
Hours					-2, 0, 2, 4, 6, 12	24 hrs	48 hrs			-2, 0, 2, 4, 6, 12	24 hrs	48 hrs					
Study drug dispensed						1 ^{a,b}					1 ^{a,b}						
Dosing compliance and dosing diary assessed									1	1	1	1			1	1	1
Sign ICF	1																
Review inclusion/exclusion criteria	1			1	1												
Medical history and demographics	1		Washout														
Diet history and counseling for (as needed) calcium intake	1																
Prior medications review	1																
Concomitant medications review	1				1	1	1	1	1	1	1	1	1	1	1	1	1
Adverse events					1	1	6	1	1	1	1	6	1	1	1	1	1
Physical exam (including weight, height and BMI)	1																1
Vital Signs Assessment	1				1	1	1	1	1	1	1	1	1	1	1	1	1
Blood pregnancy test (for females of child bearing potential)	1				1												1
Serum Hepatitis B & C/HIV screen	1																
eGFR	1																
Urinary albumin excretion	1																
Clinical chemistry (full panel)	1				1	1						1					1
Hematology	1				1	1						1					1
Clinical chemistry (partial panel)							6	1	1	1	1	6	1	1	1	1	

Confidential

	Screen	Wash out	Baseline		Treatment												EOS /ET
(Continued)																	
Visit	1		2	3	4	5	6	7	8	9	10	11	12	13	14	15	16
Week	-5		-1	-1	1	1	1	2	3	4	5	5	5	6	7	8	9
Day	-70 or -42 to - 36	-63 or -35 to -8	-7 to -2	-1	1	2	3	8	15	22	29	30	31	36	43	50	57
					(GCRC)						(GCRC)						
Hours					-2, 0, 2, 4, 6, 12	24 hrs	48 hrs				-2, 0, 2, 4, 6, 12	24 hrs	48 hrs				
Urine drugs of abuse screen	1																
CCI																	

NOTE: The number listed under each respective event reflects the number of occurrences for that specific type of event on the specific visit designations; absence of number designation indicates that no occurrence of such event is required.

^a Study drug dispensing for subjects assigned to CTAP101 Capsules and paricalcitol capsules plus low-dose cholecalciferol

^b Study drug dispensed for t=0 dose on Day 1 and 29 from monthly study drug supply.

Q [REDACTED]

APPENDIX 2 CALCIFEDIOL IR CAPSULES (HIDROFEROL)

SUMMARY OF PRODUCT CHARACTERISTICS (Translation)

